Patients will be informed that they have the right to withdraw from the study at any time for any reason, without prejudice to their medical care. The Principal Investigator also has the right to withdraw subjects from the study for any of the following reasons:

- In the event of a seizure or other AE
- Non-compliance
- Protocol violation
- Study terminated
- At discretion of PI

Risks and Benefits

Identification of Adverse Events:

An adverse event is defined as any new medical problem, or exacerbation of an existing problem, experienced by a subject while enrolled in the study, whether or not it is considered drug/device-related by the investigator.

Adverse Event Reporting

All adverse events occurring during the course of the study, whether related to Part A or Part B or otherwise, will be recorded on the Adverse Event Case Report Form. For all adverse events, the Investigator will provide an assessment of the adverse event, its treatment and resolution, and its relationship to the study. Special reporting procedures are required for certain adverse events.

Relationship of Adverse Events to the Investigational Device

The investigator will assess the relationship of the adverse event to the investigational device. The relationship will be assessed using the following categories:

- Definitely Related: A direct cause and effect relationship between the investigational drug or device/experimental treatment and the adverse event exists.
- Possibly Related: A direct cause and effect relationship between the investigational drug or device/experimental treatment and the adverse event has not been clearly demonstrated, but is likely or very likely.
- Unlikely Related: A direct cause and effect relationship between the investigational drug or device/experimental treatment and the adverse event is improbable, but not impossible.
- Unrelated: The adverse event is definitely not associated with the investigational drug or device/experimental treatment.

Unanticipated Adverse Device Effects

An unanticipated adverse device effect is defined as "any serious adverse effect on health or safety, or any life-threatening problem, or death caused by, or associated with, a device; if that effect, problem, or death was not previously identified in nature, severity, or degree of incidence in the investigational plan, or application (including supplementary application), or any other unanticipated serious problem associated with a device that relates to the rights, safety, or welfare of subjects." If an unanticipated adverse effect occurs, the investigator will promptly notify the sponsor of such an event within 24 hours of first learning of the event using the FDA MedWatch 3500A form. The form can be found online at: <https://www.fda.gov/media/69876/download>.

Protocol Title: Neuropathic Pain in Pregnancy
Institution: University of Arkansas for Medical Sciences (UAMS)
IRB Number: 204737
Sponsor: UAMS
PI: [name]

Serious Adverse Events

Each adverse event will be assessed for its seriousness using the criteria outlined below. The term serious adverse event is not synonymous with a “severe” adverse event, which may be used to describe the intensity of an event experienced by the subject. An adverse event will be classified as serious if it meets any of the following criteria:

- Results in, or contributes to, a death
- Life-threatening (i.e., the subject was, in the opinion of the investigator, at risk of death at the time of the event, but it does not include an event that, had it occurred in a more severe form, might have caused death)
- Results in a substantial disruption of a person's ability to conduct normal life functions, i.e., the adverse event resulted in a significant, persistent or permanent change, impairment, damage or disruption in the patient's body function/structure, physical activities and/or quality of life.
- Results in permanent disability or incapacity (i.e., permanent impairment of a body function or permanent damage to a body structure)
- Requires in-subject hospitalization or prolongs hospitalization
- Necessitates medical or surgical intervention to preclude a permanent disability or incapacity
- Results in a congenital anomaly or birth defect

Non-serious adverse events are all events that do not meet criteria for a “serious” adverse event.

If serious adverse event occurs, the investigator will promptly notify the sponsor of such an event within 24 hours of first learning of the event using the FDA MedWatch 3500A form. The can be found on-line at: <https://www.fda.gov/media/69876/download>

The investigator will also promptly notify the IRB of such an event as soon as possible, but no later than ten (10) working days after first learning of the event.

Severity

Each adverse event will be assessed for its severity, or the intensity of an event experienced by the subject, using the following.

- Mild: Discomfort noticed, but no disruption to daily activity.
- Moderate: Discomfort sufficient to reduce or affect normal daily activity.
- Severe: Inability to work or perform normal daily activity.

Deaths

The investigator will notify the sponsor and IRB as soon as possible, preferably within 24 hours but in no event later than 48 hours, of learning of subject's death, regardless of whether the death is related or unrelated to the investigational drug or device. The investigator will attempt to determine, as conclusively as possible, whether the death is related to the drug or device. The cause of death and the investigator's discussion regarding whether or not the death was drug- or device-related will be described in a written report.

Pre-existing conditions

Pre-existing conditions will not be reported as an adverse event unless there has been a substantial increase in the severity or frequency of the problem, which has not been attributed to natural history.

Protocol Title: Neuropathic Pain in Pregnancy
Institution: University of Arkansas for Medical Sciences (UAMS)
IRB Number: 204737
Sponsor: UAMS
PI: [name]

Eliciting and Reporting Adverse Events

The investigator will assess subjects for the occurrence of adverse events at each study visit. All adverse events (serious and non-serious) reported by the subject will be recorded on the source documents and CRFs.

Abuse of illicit or licit substances during pregnancy poses a potential risk to the subject and their pregnancy that their obstetrical and pediatric care provider should be aware. As a policy, we strongly encourage subjects to communicate this information to their obstetrical and pediatric care providers. We will only share this information with other care providers with subject's signed release of information. To the best of our knowledge, participation in part A of this study poses no risk to pregnancy and/or the infant. There may be risks, discomforts, or side effects that are not known yet. There is also the possibility of loss of confidentiality.

Risks Associated with Part A

No real risks are associated with Part A of this study other than possible loss of confidentiality. Subjects may decline to answer any questions that may make subjects uncomfortable.

Risks Associated with rTMS (Part B)

Likely: Subjects may feel anxious about participation. This typically abates after the first one or two sessions.

Less likely: Subjects may experience minor discomfort associated with head and hand muscle twitching, headache, local (head and neck), and dental pain. Head and neck pain related to stimulation of underlying muscle and nerves occurs in approximately 10% of subjects. The incidence and severity is a function of stimulus site and intensity but is most common over frontal-temporal regions. The symptoms are typically mild and limited to the time of stimulation and can be treated with acetaminophen if necessary. Subjects typically tolerate the discomfort better as session's progress. The coil position is adjusted if pain occurs. Subjects will be advised to take acetaminophen for treatment if necessary. The study physician or nurse will monitor subjects during and after each rTMS for twitching of a hand muscle, such as the abductor pollicis brevis or the first dorsal interosseous muscle, on the side of the body that is contralateral to the rTMS treatment site.

Rare: Seizure and hearing loss. The risk of having a single seizure is small, estimated at $\leq 1/10,000$ (Rossi *et al* 2009). In order to decrease this risk, subjects with preeclampsia, brain lesions, head trauma, a history of seizures (e.g., epilepsy), or taking medications known to lower seizure threshold are precluded from participating in rTMS. Study staff administering rTMS are trained in the treatment and management of an acute seizure. Life-support equipment is also readily available. All subjects will be visually monitored for signs of a seizure and/or muscle twitching throughout each rTMS treatment.

Another risk is hearing loss (temporary or permanent). To minimize this risk, subjects will wear ear plugs during rTMS. Subjects will be asked to immediately report any loosening or detachment of an earplug during treatment. Study staff will immediately stop rTMS if a subject reports or if an investigator observes that a subjects' ear plug has loosened or has fallen out.

Rare: A specific, but rare, risk of rTMS in pregnancy is inferior vena cava syndrome (or supine hypotensive syndrome). This syndrome happens in pregnancy after 24 weeks pregnant and usually occurs after laying down for about 5-10 minutes. Common symptoms are feeling dizzy

Protocol Title: Neuropathic Pain in Pregnancy
Institution: University of Arkansas for Medical Sciences (UAMS)
IRB Number: 204737
Sponsor: UAMS
PI: [name]

and/or upset to your stomach and having low blood pressure and/or high heart rate. The symptoms do not last long and usually go away when you change your position, such as lay on your left side. To decrease the chance of this happening, you will have a cushion placed under your right side during treatments when you are 24 weeks pregnant or greater.

Temporary changes in vision may be noticed immediately after rTMS. These visual changes are not thought to be actual problems with the eyes, but, rather changes in brain functioning as a result of rTMS. Things like blurred vision and/or eye floaters normalize in time. The risk will be minimized by using conservative stimulation parameters.

Facial numbness and facial nerve stimulation may also occur. Some sources estimate that 1 out of 3 individuals experience "facial twitching" during and/or after rTMS sessions. This twitching in the facial muscles is caused by intense electrical stimulation that penetrates the cortex. We will minimize this risk by using as conservative stimulation parameters as possible to meet the goals of the study.

Some patients may have fainted (syncopal/convulsive syncopal) or become lightheaded and nauseous during rTMS. We would stop TMS in case of suspected syncope. Such symptoms have been brief and resolved completely. In order to minimize risks the study doctor or nurse will use the following procedures to minimize the risks of convulsive syncope:

- Request information regarding a history of syncope during your screening process
- Monitor blood pressure during rTMS
- Monitor you for signs and symptoms of syncope appearing during rTMS and stop stimulation if signs and/or symptoms occur
- Immediately place you in a reclining position elevating your legs if signs or symptoms of syncope appear

Temporary changes in mood, such as mania and hypomania, have been caused by rTMS with high frequency stimulation. There are no reports of lasting changes in mood using the rate of stimulation that will be used in this study. To minimize this risk, subjects with a history of bipolar disorder have been excluded from participation in the study. In addition, subjects will be assessed clinically by the PI daily after each rTMS session for the development of mania or hypomania. If they develop during the study, the subject will be withdrawn from the study and referred for appropriate treatment as indicated. The PI is trained in the assessment and treatment of hypomania and mania.

Ferromagnetic pigments may interfere with rTMS treatments, and some forms of eye make-up, especially eyeliner, eye shadow and mascara, may contain ferromagnetic pigments. To minimize this occurrence, all subjects will be asked to remove all forms of eye makeup before each rTMS treatment.

The long-term effects of rTMS are unknown.

There may be benefit to subjects in this study who are participating in rTMS. For all others, taking part in this research study may not benefit the subjects personally, but we may learn new things that may be of benefit to women and children in the future.

References:

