- History of suicide attempt(s)
- Family history of epilepsy
- Heavy alcohol consumption within the past 48 hours
- Permanent makeup or tattoos with metallic dyes

Investigational Plan

The study will involve two phases - initially focusing on identification and course, followed by treatment paradigm assessment (Part A), and culminating in a pilot trial of rTMS (Part B).

Part A:

Study visits will occur approximately every 4-6 weeks during pregnancy until approximately 3 months postpartum for a maximum of 12 visits. Table 1 provides an overview of study procedures. Figure 1 illustrates subject participation and flow. In order to optimize diagnostic clarity for group assignment, we will employ a valid tool, the painDETECT Questionnaire (PDQ), for diagnostic purposes (written permission for use of PDQ has been obtained and is available upon request). The PDQ has been validated and shown high sensitivity (85%), specificity (80%), and positive predictive value (83%) (Freynhagen *et al* 2006). At study entry, subjects will complete the PDQ. Based on their scores, subjects will be separated into three groups: Group 1) subjects with NP in pregnancy (score ≥ 13); Group 2) subjects with non-neuropathic pain in pregnancy ($1 \geq \text{score} \leq 12$); and Group 3) subjects without any type of pain in pregnancy (score=0).

Other measures collected at entry include a general biographical form (WMHP Intake Form). Subjects will complete pain measures and the Beck Depression Inventory (BDI) (Beck *et al* 1960) at study entry and at each study visit. Pain measures include the Visual Analogue Scale (VAS), Pain Catastrophizing Scale (PCS) (Sullivan *et al* 1995), and measures of pain intensity, pain interference, pain behavior - all three derived from Patient Reported Outcomes Measurement Information System (PROMIS) (Amtmann *et al* 2010; Revicki *et al* 2009; Cella *et al* 2010). At each visit, the exposure tracking form will record the timing (weeks of gestation) and dosage of all

Protocol Title: Neuropathic Pain in Pregnancy
Institution: University of Arkansas for Medical Sciences (UAMS)
IRB Number: 204737
Sponsor: UAMS
PI: [name]

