- Pain Intensity Scale-Short Form 3a (Part A): This 3-item, self-report scale assesses how much a person hurts. The first 2 items assess pain intensity over the past 7 days and the last item asks the subject to rate their pain intensity "right now." The short form is not disease specific.
- Pain Catastrophizing Scale (PCS) (Part A): The PCS is a 13-item self-report scale. It asks subjects to reflect on past painful experiences, and to indicate the degree to which they experienced each of 13 thoughts or feelings when experiencing pain, on 5-point scales with the end points (0) not at all and (4) all the time. The PCS yields a total score and three subscale scores assessing rumination, magnification, and helplessness.
- painDETECT Questionnaire (PDQ) (Part A): This self-report questionnaire consists of 7 questions that address the quality of neuropathic pain syndromes. The first 5 questions ask about the gradation of pain, question 6 asks about the pain course pattern and question 7 asks about radiating pain. There are 4 additional questions which asks the subject to rate their pain now and over the last 4 weeks and to mark on a body chart if there is pain radiating into other parts of the body. These last questions are not counted in the total score.
- Exposure Tracking Form (Part A): This is a customized form used by study staff to document all exposures on a weekly basis during pregnancy and the postpartum period.
- General Biographical Form (WMHP Pain Intake Form) (Part A): All subjects will complete a WMHP-Pain intake packet, which will be composed of several sections including: 1) general

information or demographics; 2) gynecological history; 3) genetic history; 4) obstetrical history; 5) current/most recent pregnancy; 6) surgical history; 7) drug and alcohol history; 8) family medical history; 9) medical history; and 10) current status. The intake form is used at baseline and may be updated as appropriate at follow up visits.

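### A painDETECT total of 0 does not establish that a woman has no pain, so the no-pain control group may include women with non-neuropathic pain; one sign in the Group 2 limits is also reversed

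*Protocol*

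**What the plan says.** Protocol, Investigational Plan, Part A, makes the entry PDQ the sole basis for grouping: "Based on their scores, subjects will be separated into three groups". The rules are:

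- Group 1: "subjects with NP in pregnancy (score ≥ 13".
- Group 2: "subjects with non-neuropathic pain in pregnancy ($1 \geq \text{score} \leq 12", that is, 1 ≥ score ≤ 12.
- Group 3: "subjects without any type of pain in pregnancy (score=0".

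Protocol, Questionnaires and Surveys for Parts A and B, describes the instrument: "This self-report questionnaire consists of 7 questions that address the quality of neuropathic pain syndromes". It adds "The first 5 questions ask about the gradation of pain", with question 6 on course pattern and question 7 on radiation. It continues: "There are 4 additional questions which asks the subject to rate their pain now and over the last 4 weeks", together with a body chart, and then: "These last questions are not counted in the total score".

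The VAS and the PROMIS pain intensity form are also collected at entry (Protocol, Table 1), but no section uses them for group assignment. Objective II, and the four-group neonatal comparison in the Part B statistical section of both protocol and SAP, describe the comparators in terms of chronic pain. The SAP does not restate or correct the PDQ cut-offs.

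**The concern.** The questions that ask directly how much pain a woman has cannot affect whether she is called pain-free. The scored part is described as addressing the quality of neuropathic pain, so a low total is first of all evidence of few neuropathic features. The women most likely to be misplaced are those with non-neuropathic pain, who belong in Group 2.

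Group 3 is the reference for the Part A obstetrical and neonatal comparisons and for the plots by group, and it is the fourth arm of the neonatal comparison in the Part B section. If it contains women in pain, it moves towards Group 2, and the level against which neuropathic pain is judged moves as well. Part A plans 60 women with no stated split between groups, which leaves little room for such a loss.

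The Group 2 limits are a separate and smaller matter. They are the only written definition of that group, and as printed they do not describe it.

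**Working it through.** The plan gives no effect size, SD, power or group split for Part A, so there is no figure of its own to reproduce. The check is mainly logical.

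**Step 1: the rules against each possible total.** The printed Group 2 condition requires both score ≤ 1 and score ≤ 12, which reduces to score ≤ 1.

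| PDQ total | Rules as printed | First Group 2 sign reversed (1 ≤ score ≤ 12) |
|---|---|---|
| 0 | Groups 2 and 3 | Group 3 |
| 1 | Group 2 | Group 2 |
| 2 to 12 (11 values) | no group | Group 2 |
| 13 or more | Group 1 | Group 1 |

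Reversing one sign removes both the overlap and the gap. The numbers 1 and 12 are already in the right order.

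**Step 2: the Group 3 rule against the questionnaire.** Group 3 requires only that the counted items sum to 0. The ratings of pain now and over the last 4 weeks are not counted. A woman with non-zero ratings and a counted total of 0 therefore meets the Group 3 rule, under the printed limits and under the corrected ones. Correcting the inequality does not repair Group 3.

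**Step 3: effect on the contrasts.** Let μ1, μ2 and μ3 be the true group means, and suppose a fraction f of Group 3 has the Group 2 mean.

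- Observed Group 3 mean = (1 − f)μ3 + fμ2.
- Group 2 minus Group 3 = μ2 − (1 − f)μ3 − fμ2 = (1 − f)(μ2 − μ3).
- Group 1 minus Group 3 = (μ1 − μ3) − f(μ2 − μ3).

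The sample size needed to recover the same power for Group 2 versus Group 3 rises by 1/(1 − f)².

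For illustration only, assume 20 women per group (60/3), a true Group 2 versus Group 3 difference of d = 0.8 SD, a two-sided 0.05 level and a normal approximation. Power is then Φ(d(1 − f)√(20/2) − 1.96). At f = 0 this is Φ(0.8 × 3.162 − 1.96) = Φ(0.570) = 0.716. At f = 0.30 it is Φ(0.56 × 3.162 − 1.96) = Φ(−0.189) = 0.425.

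| f (assumed) | Contrast kept | Sample size factor | Illustrative power |
|---|---|---|---|
| 0 | 1.00 | 1.00 | 0.716 |
| 0.10 | 0.90 | 1.23 | 0.624 |
| 0.20 | 0.80 | 1.56 | 0.525 |
| 0.30 | 0.70 | 2.04 | 0.425 |

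If a fraction g of Group 2 is in truth pain-free, the contrast becomes (1 − f − g)(μ2 − μ3). The documents give neither f nor g.

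**The case against.** The strongest reply is that the counted items are not blind to pain. The protocol says the first five grade it and the sixth asks about its course, so a woman with clear non-neuropathic pain may well score above 0 and land correctly in Group 2. This stands. A reader might infer that a woman marking, say, 60 mm on the VAS must score 0, or that one mild symptom must score 1. The documents support neither, because they give no item wording or point values. What they support is weaker: a total of 0 does not guarantee absence of pain.

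A second reply is that the inequality is a slip. With neighbours at 0 and at 13 or more, 1 to 12 is the only sensible reading. This also stands. A reader might infer that 11 scores would go unassigned in practice, but nothing suggests the study would be run that way. The sign should also be checked against the source PDF, since it may have been altered in text extraction. Figure 1 (subject flow) was not available to me and should be checked for the group rules too.

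A third reply is about scope. Group 1 membership is unaffected, and so are the course of neuropathic pain within Group 1 and Part B's VAS and tolerability outcomes. Only comparisons that use Group 2 or Group 3 are exposed. Because pain ratings are collected at entry, misplaced women can be identified and moved. This lowers the severity, but it does not help while no document tells anyone to look.

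**Conclusion.** The Group 3 label does not follow from the Group 3 rule, by the protocol's own account of what the total contains. Some women with non-neuropathic pain may be classed as no-pain controls; the number is unknown and could be close to zero. The loss in the Group 2 versus Group 3 contrast equals f: 10% at f = 0.10 and 30% at f = 0.30. This assumes that misplaced women resemble Group 2 and that Group 2 is otherwise correct. The power figures rest on further assumptions and show only the direction and rough scale.

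The reversed sign is a genuine error in the text with an obvious intended meaning, and is unlikely to cause wrong assignment.

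This should be fixed. It does not invalidate the study: the error is confined to comparisons that use Group 2 or Group 3, its extent is unquantified, and the data needed to correct it are already on the form.

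**What to change.** Amend the protocol's group rules and repeat them in the SAP:

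- Group 1: PDQ total of 13 or more, as now.
- Group 2: PDQ total of 1 to 12, or a total of 0 with pain reported on the uncounted ratings (now or over the last 4 weeks).
- Group 3: PDQ total of 0 and no pain on those ratings.
- Print the Group 2 score limits as 1 ≤ score ≤ 12.

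Every combination of total and ratings then falls in exactly one group, and a woman with a total just below 13 cannot become a control because her ratings are 0. Re-derive the group of each enrolled woman from her stored PDQ form, and report how many move.

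Use the entry VAS only as a sensitivity check on group membership. It is also a Part A primary outcome, and defining groups by it would build in part of the difference under study.

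Reconcile the Group 3 label, which excludes pain of any kind, with Objective II and the four-group neonatal comparison, which refer to chronic pain. Ratings that reach back only 4 weeks can show that pain is present but cannot by themselves show that it is chronic, and a passing pain would count. The plan should say which contrast is meant.

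The cost is wording plus a re-check of stored forms, with no new item or visit. Group 3 becomes somewhat smaller; by how much cannot be told from the documents. Women with a total of 1 to 12 but no rated pain stay in Group 2, so any dilution from that side (g) remains and their number should be tabulated.
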